5.7 Data processing and transmission of the results

For every NIPD isolate, all typing data will be collected along with its metadata in a central database using a standardized software format (e.g. Microsoft Access), which will be password protected, with aggregated and anonymized data accessible to the participating laboratories.

6 Statistics

6.1 Calculation of the sample size

To estimate the number of samples to be sent by each hospital, we calculated a total sample size based on the main objective; estimating the proportions of circulating serotypes. Based on an estimated serotype distribution of: PCV7= 7.5%, serotype 19A= 7.5%, serotype 3 =5%, 4 additional serotypes included in vaccine PCV13 =30%, serotypes not included in the vaccine non-PCV13 = 50%, we would need a total of 2250 samples to be able to obtain these estimates within 95% confidence intervals with a width of ± 20 during the whole study period (2020-2022). This translates into approximately 2 samples per week from each hospital for the 20 months period (ie total sample size/(number of hospital*weeks of study): $2250/(12*80) \cong 2$).

For the first secondary objective (establishing a statistically significant shift in serotypes from serotypes included in the PCV-13 vaccine to serotypes not included in the PCV-13 vaccine between retrospective and prospective samples), we estimated the necessary sample size to detect a 20% decrease in PCV-13 serotypes (PCV7-serotypes, 19A, 3, 4 additional PCV13) (or 20% increase in non-PCV-13 serotypes) at n=1500 for each time point (1995-2015 and 2020-2022).

6.2 Evaluation

Our final goal is to investigate Belgian trends in serotype distribution in the non-invasive pneumococcal population. The statistical data analysis will be performed with Stat10 software (Stata Statistical Software: Release 13. College Station, TX), in collaboration with Sciensano's Epidemiology Service.

Using data from the Prospective/Retrospective surveillance track:

- Chi-square trend analysis of circulating serotypes within the non-invasive *S. pneumoniae* population, integrating retrospective data (1995-2014) with prospectively collected data (2020-2022). Data will be compared with the serotype dynamics of IPD, annually published by the NRC for pneumococcal diseases.

- Measurement of association strength within each stratum of age, gender and infection type by the prevalence ratios with exact Fisher tests for statistical significance. Particular attention will be given to NeSP isolates, their association with patient type and their influence on drug resistance.
- Chi-square trend analysis of antimicrobial resistance for all tested drug classes, in relation to historic data (1995-2013) and in association with serotype.
- Integrating metadata with WGS, we will perform phylogenetic analysis of sequenced isolates in their national and international context [13,14], and identification of genetic determinants of antibiotic resistance.

7 Access to source data and data in general

Neither of the funding partners can have a role in data collection and interpretation. However, funding partners can request at any time intermediate results or reports. The final report will be put under a six months embargo before open access publishing in Summer 2023.

8 Monitoring and quality assurance

All laboratory analyses will be performed according to ISO15089 standards. An internal project board consisting [name] (MD, PhD), [name] (Ir, PhD), [name] (Ir., PhD) and [name] (MD, PhD) will monthly follow up experimental results.

9 Adverse events

Not applicable.

10 Ethics

Upon approval of the project by at least two contact partners, a general and specific ethical application will be filed, in collaboration with Sciensano's legal department and GDPR officer. Approval of local and ethical committees will be sought.

11 Budget

PERSONNEL				
	Description	% Effort dedicated to this study	Institutional salary (3 years)	TOTAL
	Coordinating Scientist	0.6 FTE	€ 276,372	€ 165,823.2
	Statistician	0.2 FTE	-*	€ 0

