**A 20-months surveillance of non-invasive *Streptococcus pneumoniae* infections in Belgium
to evaluate national vaccination strategy**

Protocol Version 1.2

05/12/2019

0 Summary

Population	3,600 Belgian patients with community acquired pneumonia or acute otitis media, leading to positive S. pneumoniae from non-sterile clinical specimens.
Intervention	N/A
Comparison	Serotype distribution according to vaccination programs (campaigns)
Outcome	Primary: to establish insight in serotype dynamics for non-invasive pneumococcal diseases in Belgium (prospectively and retrospectively), in association with changing vaccination programs (campaigns). Secondary: surveillance of emerging serotypes, clones and drug resistances. Study of the genetic divergences between invasive and non-invasive pneumococcal diseases isolates.
Study Type	Observational

Principle Investigator [name]
Coordinating Scientist [name]
Institute Sciensano
Address [name]
Contact [contact] [contact]
[contact] [contact]

1 Study Rationale

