1.2 Changing vaccination recommendations in Belgium

In Belgium, the 23-valent polysaccharide vaccine or PPV23 (currently Pneumovax 23®, MSD) is licensed since 1995. It is currently recommended by the Superior Health Council (CSS/HGR) for the prevention of pneumococcal infections in persons ≥ 2 years of age, presenting with an increased risk of mortality and severe morbidity due to pneumococcal infections, and often sequentially combined with PCV13 (Prevenar®, Pfizer) [4]. The national infant vaccination program was initiated in 2007 with PCV7 (Prevenar®, Pfizer), and was updated to PCV13 in 2011. In 2015-2016, the program changed from PCV13 to PCV10 (Synflorix®, GSK). Very recently (HGR 9519, December 2018), a new advice was published by the Superior Health Council which recommended again the use of the 13-valent vaccine in children ≤ 2 years of age, alongside an explicit statement stating that this advice could be reconsidered upon the release of new data.

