1.4 Sciensano holds historical collection of non-invasive pneumococcal isolates

Between 1995 and 2015, [name] (MD, PhD) led a team at Sciensano investigating the evolution of antibiotic resistance in NIPD isolates from CAP patients (as well as from children with acute otitis media). For 12 consecutive winter periods, his team collected between 300 and 500 clinical isolates using a network of 15 peripheral hospital-based laboratories distributed across the country. Consequently, we hold a collection of >5,000 strains for which extracted gDNA, complete phenotypic MIC profiles and associated metadata are already available (**Figure 4** for age distribution). This study, funded by Bayer, focused on antimicrobial resistance and did not routinely include serotyping.

This constitutes an extremely valuable collection that dates from before the introduction of pneumococcal vaccination programs. In the context of the proposed study, this collection would serve to retrospectively assess the impact of successive vaccination campaigns on serotype distribution among NIPD isolates in Belgium.

[figure not shown]

Figure 4. Age distribution of the patients for which cultures were included during the NIPD surveillance study in 2012-2013 using the same network of laboratories [24].

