1.6 Key points

From the information above, it is clear that:

- Current recommendations for vaccination and empiric treatment are strongly influenced by the current surveillance focus on IPD. Information on serotype distribution and drug resistance dynamics in NIPD is scarce. However, a discrepancy in serotype distribution between IPD and NIPD isolates is present in neighbouring countries.
- In Belgium, there was a recent (2015-2016) switch in the infant vaccination program to PCV10 and a recommended reversal to PCV13 in December 2018. The influence on serotype distributions in NIPD is unclear, although this information is essential in vaccine cost-effectiveness analyses [31].

2 Study aims

The main objective of this study is to generate insight in the serotype dynamics for NIPD in Belgium, in association with changing vaccination programs. We aim to serotype non-invasive *S. pneumoniae* isolates prospectively collected in Belgian routine laboratories, during a period of 20 months. Simultaneously, a similar characterisation study will be performed retrospectively on a selection of more than 5,000 NIPD strains collected between 1995 and 2014 in Belgium.

Additionally, this projects aims to do the surveillance of emerging serotypes, clones and drug resistances. Using Whole Genome Sequencing (WGS), the genetic divergences between IPD and NIPD isolates will also be studied, in collaboration with the National Reference Centre (NRC) for pneumococcal diseases (UZ Leuven, Belgium).

3 Type of study

This will be an observational study collecting data on *S. pneumoniae* serotypes causing NIPD in Belgium, in relation with changing vaccination programs.

4 Conducting the study

The study will be conducted by Sciensano in collaboration with the NRC for pneumococcal diseases and 12 peripheral clinical laboratories, which all agreed in writing to prospectively collect non-invasive *S. pneumoniae* samples in the framework of this study. These labs are geographically spread over Belgium to avoid clonal bias in sampling (**Table 1**).

Table 1. Peripheral network of participating clinical laboratories.

Hospital	Contact	City	
CHR Citadelle	Dr. [name]	Liège	
CHU Mont-Godinne	Dr. [name]	Yvoir	
ZNA	Dr. [name]	Antwerpen	
Virga-Jessaziekenhuis	Dr. [name]	Hasselt	
Hôpital de Jolimont	Dr. [name]	Haine-St.-Paul	
AZ Delta	Dr. [name]	Roeselare	
AZ St. Jan	Dr. [name]	Brugge	
AZ. Jan Palfijn	Dr. [name]	Gent	
Imeldaziekenhuis	Dr. [name]	Bonheiden	

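### The comparison is declared by vaccination programme, but no named analysis uses programme period; the chi-square trend cannot place a shift at a programme change and can miss one that reverses

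*Protocol*

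**What the plan says.** The Summary gives the comparison as "Serotype distribution according to vaccination programs (campaigns"). Section 1.4 says the archive would serve to "retrospectively assess the impact of successive vaccination campaigns on serotype distribution among NIPD isolates in Belgium". Section 2 states: "The main objective of this study is to generate insight in the serotype dynamics for NIPD in Belgium, in association with changing vaccination programs".

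Section 1.2 dates the infant programmes: PCV7 from 2007 and PCV13 from 2011. Then "In 2015-2016, the program changed from PCV13 to PCV10", and a return to PCV13 was recommended in December 2018.

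For serotypes over time, section 6.2 names "Chi-square trend analysis of circulating serotypes within the non-invasive" population, "integrating retrospective data (1995-2014) with prospectively collected data (2020-2022"). It adds a comparison with the yearly invasive-disease data, without naming a test. Its next item is "Measurement of association strength within each stratum of age, gender and infection type", using prevalence ratios and Fisher tests. Section 6.1 sizes a shift from vaccine to non-vaccine serotypes between the two tracks "at n=1500 for each time point (1995-2015 and 2020-2022").

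**The concern.** The question concerns a sequence of dated programmes. The named test asks whether a share rises or falls steadily with time. The contrast in section 6.1 merges the years before vaccination, the PCV7 years and the PCV13 years into one group. Programme period appears in neither, and it is not among the strata listed in section 6.2.

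A significant trend would read the same whether the change came in 2007, in 2011, after 2014, or as slow drift. A serotype that rose under one programme and fell under the next could be reported as showing no trend. Any link to programme dates would then rest on looking at yearly proportions after the fact, in a study meant to evaluate the national vaccination strategy.

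**Working it through.** **Inputs from the protocol.** 150 isolates from each odd year (section 4.2). Ten odd years, 1995-2013, give 10 × 150 = 1,500, which matches the 1,500 retrospective units in the budget. The prospective target is 2,250 (section 6.1).

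**Assumptions.** Every odd year is filled, although section 1.4 counts only 12 winters. The prospective isolates are scored at 2021. Tests are two-sided at 5%. All shares are illustrative; 50% and 7.5% are starting values taken from section 6.1.

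**The plan's own figure.** As a sample size, 1,500 per time point does not follow from the listed 50% PCV13 share. A fall from 50% to 40% needs 388 per time point at 80% power. That is a separate matter, and nothing below depends on it.

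**Periods.** Before 2007: 6 × 150 = 900. 2007-2010: 300. 2011-2014/15: 300. 2020-2022: 2,250. Total 3,750.

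**Trend statistic.** Expected z = Σn(x − x̄)p / √[p̄(1 − p̄)·Σn(x − x̄)²], where x is the calendar year.

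- x̄ = (1,500 × 2004 + 2,250 × 2021)/3,750 = 2014.2
- Σn(x − x̄)² = 150 × 330 + 1,500 × 10.2² + 2,250 × 6.8² = 309,600

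*Dating.* Four different histories, all starting at 50%:

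| Path | Numerator | p̄ | Expected z |
|---|---|---|---|
| Step to 38.6% in 2007 | −1,456.9 | 0.4134 | −5.3 |
| Step to 40% in 2011 | −1,464.0 | 0.4320 | −5.3 |
| Step to 40.4% after 2014 | −1,468.8 | 0.4424 | −5.3 |
| Linear drift to 37.8% | −1,452.7 | 0.4099 | −5.3 |

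The trend test gives the same answer for all four.

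*Reversal.* Simulated power. Shares are listed in period order (before 2007 / PCV7 / PCV13 / 2020-2022). The four-period test is a chi-square with 3 degrees of freedom; the pooled contrast is 1,500 against 2,250.

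| Path (%) | Trend | Pooled contrast | Four periods |
|---|---|---|---|
| 7.5 / 14 / 7.5 / 8 | 5% | 14% | 85% |
| 50 / 50 / 40 / 50 | 6% | 22% | 81% |
| 50 / 50 / 40 / 47.5 | 21% | 6% | 75-76% |
| 50 / 50 / 40 / 45 (half reversal) | 71% | 44% | 87% |
| Lasting 10-point step in 2007, in 2011 or after 2014 | over 99% | 95% or more | over 99% |
| Linear, 50 to 45 | 57% | 50% | about 40% |

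With 1,500 or 3,600 prospective isolates, trend power under full reversal stays at 5-7%, against 80-86% for four periods.

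**What the periods can resolve.** Detectable difference at a 50% share and 80% power = 2.80 × √[0.25(1/n₁ + 1/n₂)]:

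- before 2007 against PCV7: 2.80 × √[0.25(1/900 + 1/300)] = 9.3 points
- PCV7 against PCV13: 2.80 × √[0.25(1/300 + 1/300)] = 11.4 points
- PCV13 against 2020-2022: 2.80 × √[0.25(1/300 + 1/2,250)] = 8.6 points

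**What the periods cannot do.** Under the linear drift to 37.8%, with no step at all, at least one adjacent-period contrast is significant in 50% of runs.

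**The case against.** Section 6.2 gives trends as its final goal, and section 6.1 sizes the main objective as estimation of proportions. For lasting shifts the trend test is a good choice. Yearly proportions and the invasive-disease comparison stay available, and time scores and grouping can be left to a statistical analysis plan. All this stands, and it is why the trend test should stay. It does not remove the mismatch: the protocol itself fixes a trend test for a comparison it declares by programme.

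The near-zero power needs a full return, and no share in the protocol points to one. The choice of scores matters too: rank scores raise 21% to 31% for the 50/50/40/47.5 path. The second item in section 6.2 lists strata but not the exposure, so period could be what was intended. The fair statement is that period is not named, not that it is ruled out.

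A reader might infer more in three ways, none of which is supported.

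- That the history of switching back makes a missed reversal likely. The PCV10 switch and the 2018 reversal fall almost wholly in the unsampled gap. Only the 2007 and 2011 changes lie within the archive.
- That period contrasts would attribute shifts to programmes. They also respond to drift.
- That a flagging rule could cure this, for example calling a difference programme-linked only if it appears both with and without a linear year term. Such a rule gives false flags in 21% of runs under quadratic drift and 55% under a 20-year cycle of ±5 points. It also finds a true 10-point step in 2007 only about half the time.

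**Conclusion.** The point holds as a mismatch between the declared comparison and the named analyses, and it should be fixed. The trend test is neither invalid nor weak for lasting change. Its limits are that it does not locate a shift among the programme changes, and that it loses power as a share returns towards its starting level: slightly at half reversal, almost wholly at full reversal. These sizes rest on the assumed layout, calendar-year scores and illustrative shares. Even a period comparison yields association in time only, and no analysis of these isolates can separate the PCV10 switch from the 2018 reversal.

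**What to change.** In section 6.2:

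- For each serotype group, add a comparison across programme periods (before 2007; 2007-2010; 2011-2014/15; 2020-2022). Give an overall period test and adjacent-period differences with 95% confidence intervals, shown beside the yearly proportions. Keep the chi-square trend.
- Report 2011-2014/15 against 2020-2022 beside the pooled before/after contrast.
- Add sensitivity analyses: a linear year term; boundaries moved to the next sampled year (2009, 2013); winter months only; and laboratories common to both tracks where the metadata allow. The last two are needed because the archive came from winters and 15 laboratories, while the prospective track runs every month in 12.
- Describe results as association in time, with no pass/fail rule for coinciding with a programme change.
- State that no isolates cover about 2015/16 to September 2020, so the PCV10 switch and the 2018 reversal cannot be told apart by any test.

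The cost is wording and standard analyses, with no new isolates. The period test is weaker than the trend test if change is strictly linear (about 40% against 57% for 50% to 45%). Intervals for the two 300-isolate periods will be wide, with detectable differences of about 9 to 11 points. Restricting to winter costs little: with October to March and even monthly numbers assumed, 2,250 × 12/20 = 1,350 isolates remain, and 8.6 points becomes 8.9.

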4.1 Prospective track

Regarding the prospective track (**Figure 6**), each month from September 2020 to May 2022 (20 months), twelve laboratories listed in **Table 1** committed to send the first 15 unduplicated isolates of *S. pneumoniae* collected from patients meeting the following criteria:

Inclusion criteria:

- Patients living in Belgium at the time of the study,
- from whom unduplicated *S. pneumoniae* isolates were collected in routine practices,
- from non-invasive upper (e.g.: pus/fluid from nasal sinus or from otitis media fluid) or lower respiratory tract (e.g. sputum bronchial or endotracheal aspirate, bronchoalveolar fluid (BAL),...) clinical samples.
- from patients diagnosed with pneumonia, sinusitis and otitis.

Exclusion criteria:

- Patients for whom *S. pneumoniae* was simultaneously isolated from blood or another usually sterile specimen.

Consequently, a theoretical maximal amount of 3,600 non-invasive *S. pneumoniae* isolates will be prospectively collected, although the actual number will probably be lower given the lower prevalence of NIPD during the summer period. For every shipped strain (with associated metadata) during the study period, the laboratory will be compensated by payment of €20.

The transfer of the isolates (under dry ice) from hospital laboratories to the “Sciensano Unit ‘Antibiotics & Resistance’ (Site Engeland - [name])” will be organised in the last week of every month, using the Sciensano internal sample transport service. Isolates will be accompanied by an electronic record sheet, listing the following metadata **upon availability** :

- isolate number
- Hospitalised (HOS), residing in a long-term care facility (LCF), ambulatory (AMB), or other (to be specified).
- admission date (hospitalised patients only)
- date of specimen collection
- patient age
- patient sex
- sample source including collection method
- clinical diagnosis
- vaccination status of the patient for *Streptococcus pneumoniae*
- For bacterial cultures from sputum, the amount of epithelial cells and white blood samples
- Other potential respiratory pathogens isolated (e.g. *H. influenzae*, *M. pneumoniae*, ...)

For all isolates sent, following analyses will be performed at Sciensano:

- Identification and confirmation of isolates by reference methods prior to use.
- Capsular typing using an FT-IR based method that will be developed in the scope of the project (section 5.4).

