4.3 Gantt Chart

* Intermediate reports will not be published publicly, and can only be consulted by participating hospitals and funding partners.

M1. Ethical Approval granted

M2. FT-IR based capsular typing test validated for 24 pneumococcal serotypes

M3. Protocol approved by all partners

M4. Preparatory phase finished, with Sensititre™ plates received, database and lab shipments completely prepared

M5. Capsular typing completed for selected non-invasive *S. pneumoniae* isolates (1995-2014)

M6. Capsular typing and MIC testing completed for all NIPD isolates collected during 20 months (2021-2022)

M7. Final statistical analyses on complete dataset finished

Publication 1 (provisional title): An FT-IR based test for fast *cps* typing in *Streptococcus pneumoniae*.

Publication 2 (provisional title): The genetic diversity of Belgian invasive and non-invasive *Streptococcus pneumoniae* strains in an international context.

Publication 3 (provisional title): Distribution of serotypes and drug resistance profiles of Belgian non-invasive *Streptococcus pneumoniae* strains in light of national vaccination campaigns

5 Microbiology

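### Section 6.2 handles age, sex and infection type only by separate Fisher tests within strata, with no adjusted prevalence ratio, no test of heterogeneity and no statement on crossing

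*Protocol*

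**What the plan says.** Protocol section 6.2 lists two kinds of test for the surveillance data. Changes over time are tested by "Chi-square trend analysis of circulating serotypes within the non-invasive" population, joining archive and prospective isolates; a parallel trend analysis covers resistance. Neither is described as stratified or adjusted.

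Age, sex and infection type enter through another item: "Measurement of association strength within each stratum of age, gender and infection type by the prevalence ratios with exact Fisher tests for statistical significance". The same item singles out non-encapsulated strains (NeSP), "their association with patient type and their influence on drug resistance".

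Age bands are not given. Section 4.1 supplies three infection types, since isolates come "from patients diagnosed with pneumonia, sinusitis and otitis". Section 6.1 sizes the study for overall proportions ("we would need a total of 2250 samples") and for an overall shift in PCV13 serotypes with 1,500 isolates per period. It sizes no stratum.

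**The concern.** The protocol names a specific procedure for three important covariates: estimate and test inside each stratum, then stop. Three things are missing from it.

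- **A combined estimate.** Nothing brings the strata together into one prevalence ratio adjusted for age, sex and infection type.
- **A test of heterogeneity.** A reader given one p-value per stratum will tend to take significant here and not significant there as a difference, although unequal precision or chance can produce that pattern.
- **The form of the strata.** Whether the factors are taken singly or crossed decides which weakness applies.

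The lack of adjustment matters because the two periods were sampled differently. Section 1.4 describes an archive collected in winter periods from patients with community-acquired pneumonia and from children with acute otitis media. Section 4.1 describes monthly collection from September 2020 to May 2022 from patients with pneumonia, sinusitis or otitis. If the mix of ages and infection types differs, a crude change in serotype share is partly a change in case mix.

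**Working it through.** **The plan's own figure.** The stratified item carries no number. The only test-based size is 1,500 per period in section 6.1. The PCV13 shares there add to 7.5 + 7.5 + 5 + 30 = 50%. Reading the 20% decrease as relative (50% to 40%), with two-sided 5% and 80% power assumed:

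n = [1.96·√(2·0.45·0.55) + 0.842·√(0.5·0.5 + 0.4·0.6)]² / 0.10² = 388 per period (408 with continuity correction).

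So 1,500 is not reproduced on that reading. It is matched by 20% to 16% with continuity correction (1,497). That is a separate matter; what counts here is that the sizing concerns the whole sample only.

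**Inputs for the stratum check.** 1,500 archive and 2,250 prospective isolates (6.1). Baseline 5%, the share 6.1 assumes for serotype 3; the rise to 7.5% is illustrative. Assumed: two-sided 5%, equal strata, 2 sexes, 3 infection types, 2 to 4 age bands. Singly, each factor then has 2 to 4 strata. Crossed, there are 2·2·3 = 12 to 4·2·3 = 24 cells. Section 6.2 does not name the exposure in the association, so period is used as the example.

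**Unstratified power.** Pooled proportion = (75 + 168.75)/3,750 = 0.065. Null SE = √[0.065·0.935·(1/1,500 + 1/2,250)] = 0.00822. Alternative SE = √(0.05·0.95/1,500 + 0.075·0.925/2,250) = 0.00791. Power = Φ[(0.025 − 1.96·0.00822)/0.00791] = Φ(1.125) = 0.87. Exact enumeration of the Fisher test also gives 0.87.

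**Fisher power per stratum (exact enumeration).**

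| Equal strata | Isolates per stratum | 5% v 7.5% | 50% v 40% |
|---|---|---|---|
| 2 | 750 / 1,125 | 0.57 | 0.99 |
| 3 | 500 / 750 | 0.40 | 0.93 |
| 4 | 375 / 562 | 0.31 | 0.84 |
| 12 | 125 / 188 | 0.11 | 0.40 |
| 24 | 62 / 94 | 0.05 | 0.22 |

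**What pooling recovers.** A simulated Mantel-Haenszel test on the same totals (common ratio 1.5, baselines spread over 3-7%) has power of about 0.85 to 0.86 across 4 to 24 strata, with actual size about 4%. The loss is therefore avoidable.

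**Why stratum p-values mislead.** Suppose the ratio is 1.5 in all three infection types and each stratum has power 0.40. The chance that the strata disagree on significance is 1 − 0.40³ − 0.60³ = 0.72, although there is no heterogeneity at all.

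**Confounding if factors are taken singly (illustrative figures, not from the protocol).** Let 30% of patients be children, 70% of children and 5% of adults have otitis, and a serotype's prevalence be 10% in children and 4% in adults, whatever the infection.

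- Otitis share: 0.3·0.7 + 0.7·0.05 = 0.245.
- Prevalence in otitis: (0.21·0.10 + 0.035·0.04)/0.245 = 9.1%.
- Prevalence in others: (0.09·0.10 + 0.665·0.04)/0.755 = 4.7%.
- Crude ratio: 1.94; ratio within age: 1.0.

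With 50% and 10% in place of 70% and 5%, the crude ratio is 1.57. In fully crossed strata this bias disappears, apart from what remains within broad age bands.

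**The case against.** The strongest reply is that the study's main questions do not rest on the stratified item. Changes in serotypes and in resistance have their own trend tests on the whole sample, and those keep their power. This stands: a reader might infer that the study as a whole loses most of its power, and the protocol does not support that. Nor is the loss severe everywhere, since a 50% to 40% shift in the PCV13 group is well detected in 2 to 4 strata. Low power is a problem for individual serotypes and for crossed cells.

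Second, the two harms belong to different readings. Confounding between age and infection type needs factors taken singly; the steepest power loss needs them crossed. This stands too, and the two should not be asserted together. It does not rescue the plan, because each reading has a defect and the text does not choose.

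Third, a reader might infer a flood of false positives, for instance by multiplying 24 serotypes by nine strata. The documents do not support such a count. The 24 in section 4.3 is the validation panel of the typing test, not a list of hypotheses; age bands are unstated; Fisher's test is conservative (actual size about 3-4% at 5% prevalence here); and a multiplicity rule may sit in the SAP, which is not at hand. That part is not pressed.

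Fourth, models and interaction tests are often left to an SAP. That would answer the point had section 6.2 been silent. It is not silent: it names the technique for these covariates, and the technique named is the weaker one.

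**Conclusion.** The concern holds in limited form. Section 6.2 commits to stratum-by-stratum ratios and Fisher tests as its sole treatment of age, sex and infection type, without a combined adjusted estimate or a test of heterogeneity, and leaves open how strata are formed. Taken singly, the factors stay mutually confounded. Crossed into 12 or more cells, power to detect a rise from 5% to 7.5% falls from 0.87 to about 0.1 or less per cell. On either reading, no adjusted estimate of the change between periods is produced.

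The power figures assume equal strata and two-sided 5%. Real strata will be unequal, so the largest will do better and the smallest worse. The size of the confounding cannot be known from the protocol; the ratios of 1.57 and 1.94 only show that it need not be small. The protocol shows that case mix could differ between periods, not that it does. This is a weakness in a supporting analysis that is worth correcting; it does not invalidate the trend tests.

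**What to change.** In section 6.2:

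- State the age bands and whether age, sex and infection type are crossed.
- For each serotype group, NeSP and each resistance outcome, report one adjusted prevalence ratio with 95% CI. Use a modified Poisson model with period, age group, sex and infection type, or a Mantel-Haenszel ratio for period across strata of the other three.
- Add care setting only if it is recorded in both periods. Section 4.1 lists it for prospective isolates, where available; the protocol does not say whether the archive holds it.
- Judge stratum differences by an interaction or homogeneity test, not by comparing stratum p-values.
- Keep stratum-specific ratios and Fisher tests as descriptive results, or for cells too sparse to model.

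False-discovery control across individual serotypes is optional and may be placed in the SAP.

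The cost is a few lines of text and a little more analysis. No extra isolates are needed, and age, sex and diagnosis are already on the prospective record sheet. The main drawback is that isolates with missing covariates drop out of the adjusted model, so the number excluded should be reported for each period.
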